5.4 APPENDIX 4 DATA HANDLING CONVENTIONS

Demographic formulas

Age of onset of PN is calculated as:

$$\text{Year of PN diagnosis} - \text{Year of birth}$$

BMI is calculated as:

$$\text{Weight in kg} / (\text{height}^2 \text{ in meters})$$

Renal function formulas

For adults, creatinine clearance (CLcr) value will be derived using the equation of Cockcroft and Gault:

$$\text{CLcr (ml/min)} = (140 - \text{age}) \times \text{weight (kg)} \times \frac{(1 - 0.15 \times \text{sex (0-M, 1-F)})}{(\text{creatinine} \times (\mu\text{mol/l}))}$$

CLcr will be calculated using the last weight measurement on or before the visit of the creatinine measurement and age at the lab sampling day. Here age is calculated as following:

$$\text{Age} = \text{age collected at screening} + \text{integer part of (lab sampling analysis day/365.25)}$$

Analysis windows for time points

Efficacy assessment

For the efficacy assessment, the reference date for the derivation of relative days of events or findings will be the randomization day. If a participant receives IMP prior to the randomization by mistake, the reference date of efficacy assessment will be the date of the first IMP administration for that participant.

For daily eDiary data (WI-NRS, skin Pain-NRS, Sleep-NRS), all available values of daily measurements will be assigned to each week window according to [Table 10](#), and then weekly average score will be calculated. Randomization day is used as the reference day (Day 1).

Table 10 - Time window for eDiary efficacy variables

Time	Target day	Day range for calculating weekly score
Baseline (Week 0)	1	-7- <1
Week 1	8	1-11
Week 2	15	12-18
Week 3	22	19-25
Week 4	29	26-32
Week 5	36	33-39
Week 6	43	40-46
Week 7	50	47-53
Week 8	57	54-60
Week 9	64	61-67
Week 10	71	68-74
Week 11	78	75-81
Week 12	85	82-88
Week 13	92	89-95
Week 14	99	96-102
Week 15	106	103-109
Week 16	113	110-116
Week 17	120	117-123
Week 18	127	124-130
Week 19	134	131-137
Week 20	141	138-144
Week 21	148	145-151
Week 22	155	152-158
Week 23	162	159-165
Week 24	169	166-172
Week 25	176	173-179
Week 26	183	180-186
Week 27	190	187-193
Week 28	197	194-200
Week 29	204	201-207
Week 30	211	208-214
Week 31	218	215-221
Week 32	225	222-228
Week 33	232	229-235

Time	Target day	Day range for calculating weekly score
Week 34	239	236-242
Week 35	246	243-249
Week 36	253	250-256

For other efficacy variables, all available values of scheduled measurements will be assigned to the appropriate visit window according to [Table 11](#). In the event of multiple measurements of the same test in the same window, the one closest to the targeted visit date will be used for the by-visit summary. If they are at the same number of days away from the target day, the latest one will be used.

Table 11 - Time window for efficacy variables

Visit	Target Day	Time windows for				
		DLQI, IGA PN-A/PN-S	HADS, EQ-5D-5L, Missed school/work days	PGIS	PGIC	PAS
Visit 1 (Week -4 to -2)	<1			<-14		<-14
Visit 2 (Week 0)	1	1-	1-	-14-1-		-14-1-
Visit 3 (Week 4)	29	1+-42		1+-42	1+-42	1+-42
Visit 4 (Week 8)	57	43-70		43-70	43-70	43-70
Visit 5 (Week 12)	85	71-126	1+-126	71-126	71-126	71-126
Visit 6 (Week 24)	169	127-210	127-210	>126	>126	127-210
Visit 7 (Week 36)	253	>210	>210			>210

1-: up to randomization and before 1st dose date/time; 1+-: after randomization or 1st dose date/time

Safety assessment

For the safety assessment, the reference date for the derivation of relative days of events or findings will be the date of first IMP administration. Selected safety variables will be summarized by the analysis window define in [Table 12](#) for the by visit descriptive analysis. All available values from central lab will be assigned to the appropriate visit window. In the event of multiple measurements of the same test in the same window, the one closest to the targeted visit date will be used for the by-visit summary. If they are at the same number of days away from the target day, the latest one will be used. For procedures planned on Visit 2, if it is done on the same date as the first IMP injection but the performance time is missing, it will belong to Visit 2 time window.

Table 12 - Time window for safety endpoints

Visit	Target Day	Time windows for							
		Vital signs	Hematology, biochemistry	Urinalysis	CD4 T cell count and HIV test	Serum Pregnancy test	Urine Pregnancy test	Physical examination	ECG
Visit 1 (Week -4 to -2)	<1	<-14	<-14	<-14	1-	<-14		<-14	1-
Visit 2 (Week 0)	1	-14-1-	-14-1-	-14-1-			-14-1-		-14-1-
Visit 3 (Week 4)	29	1 ⁺ -42	1 ⁺ -42	1 ⁺ -42			1 ⁺ -42		
Visit 4 (Week 8)	57	43-70	43-70	43-70			43-70		
Visit 5 (Week 12)	85	71-126	71-126	71-126			71-126		
Visit 6 (Week 24)	169	127-210	127-210	>126	1 ⁺		127-210	1 ⁺ -210	1 ⁺
Visit 7(Week 36)	253	>210	>210				>210	>210	

1-: up to 1st dose date/time; 1⁺: after 1st dose date/time;

Pharmacokinetics/pharmacodynamics assessment

For the pharmacokinetics/pharmacodynamics variables summary, the reference date for the derivation of relative days of measurements will be the date of first IMP administration if the participant is treated with study treatment, or the randomization date if the participant is not treated. Pharmacokinetics/pharmacodynamics variables will be summarized by the analysis window defined in [Table 13](#) for the by visit descriptive analyses. All available values of measurements will be assigned to the appropriate visit window. In the event of multiple measurements of the same test in the same window, the one closest to the targeted visit date will be used for the by-visit summary. If they are at the same distance to the target day, the latest one will be used. For procedures planned on Visit 2, if it is done on the same date as the first IMP injection but the performance time is missing, it will belong to Visit 2 time window.

Table 13 - Time window for pharmacokinetics/pharmacodynamics variables

Visit	Target day	Time windows for		
		Serum dupilumab concentration	Anti-drug antibodies	Total IgE
Visit 1 (Week -4)	<1			
Visit 2 (Week 0)	1	1-	1-	1-
Visit 3 (Week 4)	29	1 ⁺ -42		1 ⁺ -42
Visit 4 (Week 8)	57	43-70		43-70
Visit 5 (Week 12)	85	71-126	1 ⁺ -126	71-126
Visit 6 (Week 24)	169	127-210	127-210	127-210
Visit 7(Week 36)	253	>210	>210	>210

1⁺: up to 1st dose date/time or randomization if participant is not treated; 1⁺: after 1st dose date/time or randomization date if participant is not treated;

Unscheduled visits

Unscheduled visit measurements of laboratory data, vital signs, and ECG will be used for computation of baseline, the last on-treatment value, analysis according to PCSAs, and the shift summaries for safety. They will also be included in the by-visit summaries if they are re-allocated to scheduled visits.

5.5 APPENDIX 5 SAMPLE SAS CODE

The multiple imputation and analysis model for the primary analysis of change from baseline in WI-NRS at Week 24 will be built with the following sample SAS code.

1. 40 datasets with a monotone missing pattern will be obtained, induced by Markov Chain Monte Carlo (MCMC) method on participants who have not taken the prohibited medications and/or rescue medications or have discontinued study treatment due to lack of efficacy prior to Week 24.

```
proc mi data=dat_etd seed=16460 n impute=40 out=dat_mc;  
  mcmc impute=monotone;  
  var atopicyн stableyn region antidblyn trt01p winrsbl chglwinrs ...  
    chg24winrs;  
run;
```

2. For each of the imputed dataset with monotone missing pattern in step 1, the remaining missing data will be imputed using the regression method for the monotone pattern with adjustment for covariates including intervention groups, documented history of atopy (atopic or non-atopic), stable use of TCS/TCI (yes or no), region, baseline anti-depressant use (yes or no), and baseline value of the response variable.

```
proc mi data=dat_mc n impute=1 seed=16461 out=dat_mi;  
  by _imputation_;  
  class atopicyн stableyn region antidblyn trt01p;  
  monotone method=reg;  
  var atopicyн stableyn region antidblyn trt01p winrsbl chglwinrs ...  
    chg24winrs;  
run;
```

3. Each of the 40 imputed datasets will be merged with the one dataset imputed by WOCF approach, and then be analyzed using the main statistical model. These 40 imputed datasets will be saved.

```
%macro w1;  
  %do i=1%to 40;  
    data wocf&i.;  
    set wocf;  
    _imputation_=&i.;  
    run;  
  %end;  
  data wocf_all;  
  set %do j=1 %to 40; wocf&j. %end;;  
  run;  
%mend w1;  
  
%w1  
  
data dat_imp;  
  set dat_mi  wocf_all;  
Run;  
  
proc sort data=dat_imp;  
  by _imputation_;  
run;  
  
proc glm data= dat_imp;  
  by _imputation_;  
  class atopicyн stableyn region antidblyn trt01p;
```

```
model chg24winrs = atopicyn stableyn region antidblyn
   trt01p winrsbl;
lsmeans trt01p / stderr;
estimate 'Diff Dupilumab vs Placebo' trt01p -1 1;
ods output LSMeans=implsmeans Estimates=implsmeandiff;
run;
```

4. Applying Rubin's rule to combine analysis results (point estimates and standard errors) from 40 imputations using PROC MIANALYZE for the LS means and difference in LS means between dupilumab and placebo. Sample code:

```
proc sort data=implsMeans; by trt01pn _imputation_; run;

proc mianalyze data= implsmeans;
   by trt01pn;
   modeleffects lsmean;
   stderr stderr;
   ods output ParameterEstimates=lsmeans;
run;

proc mianalyze data=implsmeandiff;
   modeleffects estimate;
   stderr stderr;
   ods output ParameterEstimates=lsmeandiff;
run;
```

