2 SAMPLE SIZE DETERMINATION

The primary endpoint is the proportion of participants with WI-NRS reduction of ≥ 4 from baseline to Week 24. By assuming the response rate is [REDACTED] in the placebo and dupilumab arms, respectively, 56 participants/arm will provide 90% power to detect the difference of [REDACTED] between dupilumab and placebo with Fisher exact test at 2-sided level of 0.05. Assuming 15% drop out during treatment, the target is to randomize 75 participants/arm with a cap of up to 10% of participants in the atopic population having active mild AD.

The assumptions were based on the effect of dupilumab versus placebo in WI-NRS reduction ≥ 4 at Week 16 observed in participants with moderate to severe AD as seen in studies of AD-1334 (Solo1) and AD 1416 (Solo2).

Approximately 150 participants will be randomized to dupilumab or placebo in a 1:1 ratio with stratification factors of documented history of atopy (atopic or non-atopic), stable use of TCS/TCI (yes or no), and country/territory code. Both the atopic and the non-atopic PN population will be capped at 60% of the total enrolled population.

The sample size calculation was performed using SAS 9.4 power procedure.

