The primary estimand for continuous secondary efficacy endpoints is defined in [Table 3](#) and will be analyzed using an analysis of covariance (ANCOVA) model with intervention group, documented history of atopy (atopic or non-atopic), stable use of TCS/TCI (yes or no), region (countries combined), baseline antidepressant use (yes or no), and relevant baseline measurement as covariate, with intercurrent event strategy and missing data handling as defined as in [Table 3](#). Specifically, data of participants taking the prohibited medications/procedures and/or rescue medications will be set to missing after the medication usage, and the worst postbaseline value on or before the time of the medication usage will be used to impute missing endpoint value (for participants whose postbaseline values are all missing, the baseline will be used to impute). Participants who discontinue the treatment prematurely are encouraged to follow the planned clinical visits and in those participants who did not take the prohibited medications/procedures

and/or rescue medications, all data collected after treatment discontinuation will be used in the analysis. For these participants, missing data may still happen despite all efforts have been tried to collect the data after treatment discontinuation. For participants who discontinue due to lack of efficacy, all data collected after discontinuation will be used in the analysis, and a WOCF approach will be used to impute missing data if needed. For participants who discontinued not due to lack of efficacy, a multiple imputation (MI) approach will be used to impute missing endpoint value, and this MI method will use all participants excluding participants who have taken the prohibited medications/procedures and/or rescue medications prior to timepoint of endpoint of interest and excluding participants who discontinue due to lack of efficacy.

Each of the imputed complete data will be analyzed by fitting an ANCOVA model as described above. The imputation number will be about 40. Statistical inference obtained from all imputed data will be combined using Rubin's rule. Descriptive statistics including number of participants, mean, standard error, and least squares (LS) mean changes (and standard error) will be provided. In addition, difference of the dupilumab group against placebo in LS means and the corresponding 95% confidence intervals (CI) will be provided along with the p-values.

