4.6 MULTIPLICITY ISSUES

The multiplicity procedure is proposed to control the overall type-I error rate for testing the primary and selected secondary endpoints. The overall alpha is 0.05. The comparisons with placebo will be tested based on the hierarchical order below at 2-sided $\alpha = 0.05$:

In US and US reference countries:

- Proportion of participants with improvement (reduction) in WI-NRS by ≥ 4 from baseline to Week 24
- Proportion of participants with IGA PN-S 0 or 1 score at Week 24
- Proportion of participants with both an improvement (reduction) in WI-NRS by ≥ 4 from baseline to Week 24 and an IGA PN-S 0 or 1 score at Week 24
- Percent change from baseline in WI-NRS at Week 24
- Change from baseline in HRQoL, as measured by Dermatology Life Quality Index (DLQI) to Week 24
- Change from baseline in skin Pain-NRS to Week 24
- Change from baseline in Hospital Anxiety and Depression Scale (HADS) total score to Week 24

In all other countries (including EU and EU reference countries, as well as Japan):

- Proportion of participants with improvement (reduction) in WI-NRS by ≥ 4 from baseline to Week 24
- Proportion of participants with IGA PN-S 0 or 1 score at Week 24
- Percent change from baseline in WI-NRS at Week 24
- Change from baseline in HRQoL, as measured by Dermatology Life Quality Index (DLQI) to Week 24
- Change from baseline in skin Pain-NRS to Week 24
- Change from baseline in Hospital Anxiety and Depression Scale (HADS) total score to Week 24.

The study is considered positive when the primary endpoint achieves statistical significance.

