		To reflect that the primary endpoint timepoint is Week 24.	To maintain consistency in language with the change in the primary endpoint.
		To update Table 6 to reflect that the primary endpoint is assessed at Week 24.	To maintain consistency in language with the change in the primary endpoint.
		To remove the possibility of re-evaluating the timing of the primary database lock of EFC16459 based on the observed treatment effect size in EFC16460, that was added per Amendment 02. And to consequently remove the 2 populations (ITT-Week 12 and ITT-Week 24) that were added per Amendment 02.	Amended protocol 02 was submitted in few countries but was withdrawn following a Health Authority feedback and was not implemented in any country.
		Subsection 10.12.2 was added and the overall rationale and table with summary of changes for Amended protocol 02 were moved from the cover page to this section.	This is aligned with Sanofi procedures.

5.3 APPENDIX 3 DEMOGRAPHICS AND BASELINE CHARACTERISTICS, PRIOR OR CONCOMITANT MEDICATIONS/PROCEDURES

Demographics, baseline characteristics, medical surgical history

The following demographics and baseline characteristics, medical and surgical history and disease characteristics at baseline will be summarized using descriptive statistics in the randomized population.

Demographic variables are

- Age in years (quantitative and qualitative variable: 18-<40, 40-<65, 65-<75, and ≥ 75 years),
- Gender (Male, Female),
- Race (White, Black or African American, Asian, American Indian or Alaska Native, Native Hawaiian or other Pacific Island, unknown),
- Ethnicity (Hispanic or Latino, Not Hispanic or Latino, Unknown),
- Region (Asia: Japan, China, South Korea; East Europe: Russia; Latin America: Argentina, Mexico; Western Countries: USA, France),

- Territory (North America: USA; European Union: France; Rest of World: Russia, Japan, China, South Korea, Argentina, Mexico),
- Weight in kg (quantitative and qualitative variable: (<60, \geq 60- <90, \geq 90 kg),
- BMI in kg/m² (quantitative and qualitative variable: (<25, \geq 25- <30, \geq 30 kg/m²).

Baseline safety and efficacy parameters (apart from those listed above) will be presented along with the safety and efficacy summaries.

Medical (or surgical) history includes all the relevant medical (or surgical) history during the lifetime of the participant.

This information will be coded using the version of MedDRA currently in effect at Sanofi at the time of database lock.

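### The sample code pools the imputed ANCOVA results with near-infinite degrees of freedom, so the four continuous hierarchy endpoints are tested at about 5.2% instead of 5%

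*SAP*

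**What the plan says.** SAP Section 4.6 sets the level for the hierarchy: "The overall alpha is 0.05", two-sided, in a fixed order. Both regional sequences contain the same four continuous endpoints after the binary ones: percent change in WI-NRS, and change in DLQI, skin Pain-NRS and HADS total score, all at Week 24.

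For continuous endpoints, SAP Section 4.4.2 specifies an ANCOVA on about 40 imputed datasets and says: "Statistical inference obtained from all imputed data will be combined using Rubin's rule". It gives no rule for degrees of freedom and refers to Section 5.5 for the code. Section 4.5.2 gives skin Pain-NRS and HADS, which are listed as exploratory, the same method.

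In Section 5.5, step 3 fits PROC GLM to each imputed dataset. Step 4 pools the LS means in one PROC MIANALYZE call and the treatment difference in another, "proc mianalyze data=implsmeandiff". Each call has only MODELEFFECTS and STDERR. Neither has EDF=, and the PROC GLM error degrees of freedom are not passed on.

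**The concern.** With EDF= omitted, the reference degrees of freedom depend only on the number of imputations and the between-imputation share of the variance. With 40 imputations and modest missing data they run from about a thousand to nearly a hundred thousand. The uncertainty in the residual variance, estimated from about 150 participants, is ignored. With complete data the same ANCOVA would use a t distribution on 141 degrees of freedom, so losing data appears to add precision to the reference distribution.

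Each pooled p-value is therefore slightly too small and each 95% interval slightly too short, always in the same direction. Four of these tests carry confirmatory claims. The same holds for every other continuous endpoint analysed with this code.

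**Working it through.** **Inputs**

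- Sample size: "Approximately 150 participants will be randomized to dupilumab or placebo in a 1:1 ratio" (SAP Section 2).
- Imputations: "40 datasets with a monotone missing pattern will be obtained" (SAP Section 5.5), so m = 40.
- Model: "model chg24winrs = atopicyn stableyn region antidblyn" plus treatment and baseline (SAP Section 5.5).
- Region has four levels, hence 3 parameters: "Region (Asia: Japan, China, South Korea; East Europe: Russia; Latin America: Argentina, Mexico; Western Countries: USA, France" (SAP Section 5.3, Appendix 3).
- λ, the between-imputation share of the total variance, is not in the documents. I use 0.02 to 0.20 as the main range and extend it to 0.30. "Assuming 15% drop out during treatment" (SAP Section 2), together with the use of off-treatment data, makes 0.05 to 0.15 plausible.

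**Complete-data degrees of freedom**

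Parameters: intercept 1 + atopy 1 + TCS/TCI 1 + region 3 + antidepressant 1 + treatment 1 + baseline 1 = 9. So ν₀ = 150 − 9 = 141.

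**Formulas**

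- As coded (ν₀ infinite): ν_m = (m − 1)/λ² = 39/λ².
- Small-sample (Barnard-Rubin): ν_obs = (ν₀ + 1)/(ν₀ + 3) × ν₀ × (1 − λ) = (142/144) × 141 × (1 − λ), then ν = 1/(1/ν_m + 1/ν_obs).
- Actual size = 2 × P(t on ν > critical value as coded).
- Narrowing = 1 − (critical value as coded)/(critical value on ν).

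Example, λ = 0.10: ν_m = 39/0.01 = 3,900; ν_obs = 139.04 × 0.90 = 125.1; ν = 1/(1/3,900 + 1/125.1) = 121.2.

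**Results, N = 150**

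| λ | df as coded | df adjusted | critical value as coded | critical value adjusted | actual size | interval too narrow by |
|---|---|---|---|---|---|---|
| 0.02 | 97,500 | 136.1 | 1.960 | 1.978 | 5.20% | 0.89% |
| 0.05 | 15,600 | 131.0 | 1.960 | 1.978 | 5.21% | 0.92% |
| 0.10 | 3,900 | 121.2 | 1.961 | 1.980 | 5.22% | 0.97% |
| 0.20 | 975 | 99.8 | 1.962 | 1.984 | 5.25% | 1.09% |
| 0.30 | 433 | 79.5 | 1.966 | 1.990 | 5.28% | 1.25% |

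With nothing missing (λ = 0), the code uses 1.960 where the ANCOVA itself uses 1.977 on 141 degrees of freedom, and the size is 5.20%. The SAP's 5.0% is recovered only with the adjusted degrees of freedom.

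**Other sample sizes, λ from 0 to 0.30**

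- 128 analysed (15% fewer): size 5.23% to 5.34%, narrowing 1.0% to 1.5%.
- 160 analysed: size 5.18% to 5.27%, narrowing 0.8% to 1.2%.

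**Simulation under the null**

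About 60,000 trials per scenario, with N = 150, the nine-parameter ANCOVA, m = 40 and normal residuals. The Monte Carlo standard error is 0.0009.

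| Scenario | Size as coded | Size with EDF = 141 |
|---|---|---|
| no multiple imputation, 10% WOCF | 0.0522 | 0.0501 |
| 10% multiple imputation, 10% WOCF | 0.0512 | 0.0490 |
| 15% multiple imputation, no WOCF | 0.0533 | 0.0510 |

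The paired difference is 0.0021 to 0.0023 in all three, and the mean narrowing is 0.87% to 0.96%.

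**The case against.** The case for leaving the code alone has several parts.

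- **It is Rubin's rule.** Infinite complete-data degrees of freedom is the rule's original form, so the code does not contradict Section 4.4.2. That is true. But this form presumes a large complete-data sample, and here the error degrees of freedom are finite and known.
- **It is only sample code.** It is schematic: a variable list is abbreviated, and the treatment variable's name changes between steps 3 and 4. The production program may differ. However, Section 5.5 says the analysis will be built with this code, and nothing else in the SAP says how the pooled test is referred to a distribution.
- **The printed code is for another endpoint.** It handles absolute change in WI-NRS at Week 24, which is in neither hierarchy. It reaches the four endpoints through Sections 4.4.2 and 4.5.2. That route is indirect but clear.
- **The consequence is very small.** The primary and key secondary main analyses are CMH tests with non-responder imputation and no pooling, and study success rests on the primary endpoint alone. The continuous endpoints are tested only after every binary test succeeds, so familywise error reaches about 5.2% to 5.3% at most, and only if the binary effects are real. A conclusion would change only for a coded p-value between roughly 0.0475 and 0.050. In the simulation closest to the planned hybrid method (10% each of multiple imputation and WOCF), the coded size was 0.0512, within about 1.3 standard errors of 0.05. What does not go away is the paired gap, which was the same in every scenario.

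These points limit the weight of the concern. They do not justify a pooled test with more degrees of freedom than the complete-data test.

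**Conclusion.** The concern holds. As written, the code tests the four continuous hierarchy endpoints at about 5.2% (5.20% to 5.25% for λ of 0.02 to 0.20) and gives 95% intervals about 1% too narrow (0.9% to 1.1%). The effect is minor, systematic and liberal, and it leaves the primary and key secondary conclusions untouched.

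The conclusion rests on four assumptions: PROC MIANALYZE takes infinite complete-data degrees of freedom when EDF= is omitted (a software default that the documents do not state); about 150 participants and four regions are analysed; λ lies in the assumed range; and residuals are roughly normal. The direction does not depend on λ. For bounded scores that include singly imputed WOCF values, the exact sizes are approximate.

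**What to change.** Add EDF= to both PROC MIANALYZE calls in step 4 of SAP Section 5.5, set to the error degrees of freedom of the PROC GLM fit for that endpoint: 141 with 150 participants and four regions, otherwise the actual value. State in Section 4.4.2 that pooled inference uses the small-sample adjusted degrees of freedom.

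The cost is one option in two lines and one sentence of text. P-values and intervals become very slightly less favourable; for an endpoint with 80% to 90% power, the loss is about 0.3 to 0.5 percentage points. The change should be made before unblinding, because a choice of degrees of freedom that decides a borderline result would look post hoc afterwards.
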